**Sample size.** The estimated sample size has been calculated using the statistical package G\*Power 3.1.9.4 (version 2019) for a multivariate analysis of variance (MANOVA) according to the effect size (Cohen's  $d$ ) (between 0.43 and 0.59) of anxiety in previous study on group music-guided imagery (Torres et al., 2018). When converting to a repeated measure (Cohen's  $f$ ), the effect size is considered moderate ( $f = 0.25$ ), with a type I error rate of 5% (2-sided) and assuming a correlation of 0.5 between repeated measures. To achieve 90% power to measure outcome three times in two groups, 232 subjects ( $n=116$  per group) will be required (Cohen, 1988). Assuming a 20% attrition rate (Porter et al., 2012), the trial will require at least 145 participants starting in each arm. We target to complete the recruitment process within 20 weeks; therefore, an average rate of recruitment about 14 subjects per week is anticipated. It might be possible to shorten the recruitment period if the threat posed by the pandemic weakens.

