**Control group.**

Participants (6-8 participants per group) will receive a 30-minute Mental Health Education Programme (MHE) in the first meeting (week 1) and second meeting (week 6). The content of the MHE is adopted from the Student Health Service, Department of Health, HKSAR. The MHE is comprised of the following topics:

What is Stress?

[https://www.studenthealth.gov.hk/english/health/health\\_ph/health\\_ph\\_stress.html](https://www.studenthealth.gov.hk/english/health/health_ph/health_ph_stress.html));

Tips on Being Joyful

<https://www.chp.gov.hk/archive/joyful/en/contentsab5e.html?id=40>);

Breathing Exercise practice

[https://www.studenthealth.gov.hk/english/emotional\\_health\\_tips/eh\\_tips/eh\\_tips.html](https://www.studenthealth.gov.hk/english/emotional_health_tips/eh_tips/eh_tips.html));

and

Music listening.

A take home kit which consists of the fact sheet information of the health talk and the video link of the breathing exercise and musical pieces will be provided to the participants after the first meeting. They are instructed to practice the breathing exercise and listening to the musical pieces at home. A weekly reminder via WhatsApp message and email will be sent to the participants to enhance their compliance. In the second meeting, participants will receive the revision talk about on the MHE and share their experience in stress management with the group members.

**Treatment Fidelity.** To ensure treatment fidelity, the certified music therapist will have at least 25 hours of MB programme training; the implementation of the intervention will be supervised by [name], the Co-I. The group sessions will be audio-taped with the consent of the participants, and the recordings will be given to the supervisor for quality monitoring. Written session reports will be provided and regular meetings via Zoom (i.e., three supervisions in the first group, and then two supervisions in the subsequent groups) will be arranged for maintaining the quality of the intervention. The research team will discuss any issues that may arise regarding the study protocol to ensure the quality and consistency of study intervention via regular face-to-face or online meetings.

**Measures.** Primary and secondary measures will be collected at before-intervention (T0), after-intervention (week 6; T1) and 1-month follow-up (week 10, T2) via a self-administered questionnaire. The salivary cortisol levels will be collected at T1.

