**Primary outcome**

***Sense of coherence.*** The 13-item Chinese version of the Sense of Coherence Scale (C-SOC-13) (Ding et al., 2012) will be used to measure the comprehensibility, manageability and meaningfulness of the participants' lives (Antonovsky, 1993). This

scale is scored on a 7-point semantic scale with two anchoring phrases, ranging from 1 (very poor) to 7 (very strong). The higher mean score represents a greater sense of coherence. The original SOC-13 was shown to have high internal consistency (Cronbach's  $\alpha = .74 - .91$ ) (Antonovsky, 1993).

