**Statistical analysis.** The statistical analysis will be performed in accordance with the study design, RCT with an intention-to-treat analysis using SPSS, Version 26. The baseline characteristics of the participants in the two arms will be compared to identify any clinically meaningful differences at baseline and at each time point using Chi-square test (for nominal data), Mann-Witney U test (for ordinal or non-normality data) or t-test (for normality data). Any variables considered to be significantly different will be further evaluated (e.g., included as covariates in the statistical analyses) and adjusted to account for their potential confounding effects on the outcomes. To measure both the primary and secondary outcomes, we will obtain repeated measures of multiple outcomes in the two groups, and the data will be analysed using a multivariate approach, such as a MANCOVA or Generalized Estimating Equation (GEE), with adjustment of the baseline outcome variables to test for between-group differences. Correlation analyses will be performed to determine the relationships among the dependent variables. Regression analyses and ANOVA will be conducted to assess significant differences in the effects of the demographic variables on each outcome variable. Repeated measures of ANOVA will be performed to explore the levels of sCort differing within subjects and between groups; between the two sampling days (day) and across the five sampling times (time). Path analyses will be conducted to test the mediating effects between stress-related symptoms and personal strength and emotional regulation. Sub-group analyses will be conducted according to categorisations such as

gender, coping style and religion.

**Ethical considerations.** Ethical clearance will be sought prior to the study from the study institution. Consent will be obtained and anonymity ensured to protect privacy. Participants will receive study information and have autonomy to withdraw from the study at any time.

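### Sense of coherence, the only primary outcome, has no single fixed analysis: model, deciding contrast, time point and missing-data rule are open, and one permitted method drops incomplete cases

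*Combined protocol and SAP*

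**What the plan says.** The Primary outcome section names one primary measure, "The 13-item Chinese version of the Sense of Coherence Scale (C-SOC-13"). The Measures section sets the schedule: "Primary and secondary measures will be collected at before-intervention (T0), after-intervention (week 6; T1) and 1-month follow-up (week 10, T2"). SOC therefore has two post-baseline values per participant.

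The Statistical analysis section describes the trial as an "RCT with an intention-to-treat analysis using SPSS, Version 26". Primary and secondary outcomes then share one sentence on method: "the data will be analysed using a multivariate approach, such as a MANCOVA or Generalized Estimating Equation (GEE"). On the comparison itself, that sentence adds only that it is made "with adjustment of the baseline outcome variables to test for between-group differences". No sentence deals with SOC alone.

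The Sample size section plans "with a type I error rate of 5% (2-sided") and 90% power, "assuming a correlation of 0.5 between repeated measures". It arrives at 232 evaluable participants. "Assuming a 20% attrition rate", it raises this to at least 145 per arm.

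Two features of the analysis are therefore fixed: arms are compared, and baseline values are adjusted for. Four are not: the model, the contrast (average group effect, group-by-time interaction, or a difference at one visit), the deciding visit, and the handling of missing T1 or T2 values. Hypothesis H1 groups SOC with three other scales and gives no time point.

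**The concern.** Several different analyses would all comply with this text, and they differ in who is analysed and in what error rate applies.

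- **Population.** MANCOVA needs a complete set of responses. Run in the usual way, it deletes anyone with a missing T1 or T2 value, including people who did give T1. This is a property of the method, not a statement in the document. The result is a complete-case analysis, which conflicts with the intention-to-treat promise.
- **Error rate.** With no contrast or visit named, a positive SOC claim could rest on T1, on T2, or on whichever succeeds. The Study design section blinds the data analyst to allocation, but that does not hide which visit reaches significance.

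At stake are the two-sided 5% error rate, freedom from bias due to selective loss, and SOC data already collected.

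**Working it through.** **1. The plan's own figures.** Inputs from the Sample size section: f = 0.25, two-sided 5%, 90% power, three measurements, two groups, correlation 0.5, attrition 20%.

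- A MANOVA global test with 3 responses has noncentrality N × f² = 232 × 0.0625 = 14.5 on 3 and 228 degrees of freedom. Power is 0.902, so 232 reproduces. The stated correlation of 0.5 plays no part in this formula.
- A repeated-measures between-group test does use the correlation: noncentrality = N × f² × 3 / (1 + 2 × 0.5). It needs 116 in total.
- A MANOVA group-by-time test with noncentrality N × f² needs 206.
- Attrition: 116 / (1 − 0.20) = 145 per arm, or 290 in total. This reproduces.

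The figure 232 is not in dispute. The stated inputs fit more than one test, so the sample size does not tell the reader which contrast decides the trial.

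**2. Who is dropped.** Take attrition to mean lacking a complete T1 and T2.

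- Dropped by complete-case MANCOVA: 290 × 0.20 = 58, leaving 232.
- If 25–75% of losses come after T1 (assumed), those with a T1 value are 58 × 0.25 = 14.5 to 58 × 0.75 = 43.5, about 15–44 people.
- A model on all available data analyses 232 + 14.5 = 246.5 to 232 + 43.5 = 275.5, about 247–276 people.
- The rest of the 58 have no post-baseline SOC under any model.

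Power is not the issue, because 232 was raised to 290 for this loss.

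**3. Bias, as an illustration.** The following assumptions are not in the document: no true effect; all correlations 0.5; 20% total loss; loss before T1 random; loss after T1 in the MB arm with odds 2 or 3 times higher per 1 SD lower T1 SOC, and random in control. There were 8,000 simulated trials per setting. The results are for the complete-case T1 difference.

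| Share of losses after T1 | Bias, odds ratio 2 | Rejection | Bias, odds ratio 3 | Rejection |
|---|---|---|---|---|
| 25% | 0.028 SD | 5.9% | 0.046 SD | 6.8% |
| 50% | 0.055 SD | 7.9% | 0.082 SD | 11.0% |
| 75% | 0.079 SD | 10.5% | 0.117 SD | 18.0% |

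Using all T1 data, bias stays within 0.003 SD and rejection is 4.6–5.4%. At T2 the completers-only estimate, which is what unweighted GEE gives under an independence working correlation, is biased by 0.011–0.041 SD. The likelihood model, and GEE with an exchangeable working correlation, stay within 0.003 SD.

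**4. Type I error if either visit counts.** With all pairwise correlations 0.5, the T1–T2 correlation after adjusting for T0 is (0.5 − 0.25) / (1 − 0.25) = 0.333. Error in either direction is 1 − P(|Z1| < 1.96 and |Z2| < 1.96). A false claim favouring MB is 1 − P(Z1 < 1.96 and Z2 < 1.96), with nominal rate 2.5%.

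| Correlation of the two tests | Either direction | Favouring MB |
|---|---|---|
| 0 | 9.8% | 4.9% |
| 0.333 | 9.5% | 4.7% |
| 0.5 | 9.1% | 4.5% |
| 0.7 (assumed) | 8.3% | 4.2% |

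If a joint T1/T2 test at 5% must be significant first, the overall error cannot exceed 5%, because no claim can be made without that test.

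**The case against.** The strongest reply is that the plan is less open than this suggests. It names two candidate methods, a between-group comparison and baseline adjustment. Its sample size reproduces as a single MANOVA test, which leans towards one joint analysis. That stands against a reader who infers that there is no analysis plan at all. It does not supply a contrast, a deciding visit or a missing-data rule.

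Other stronger readings also fail:

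- **That the trial runs at nearly 10% type I error.** This needs two ungated tests with success on either, which the plan does not propose. Naming T1 or T2 in advance, or gating with a joint test, removes the excess. The 8.3–9.8% also counts findings in both directions.
- **That 58 participants' outcomes are recoverable, or that power is lost.** Only those with a T1 value can be recovered, and that number rests on an assumed split. Power was protected by the inflation.
- **That the result will be biased towards MB.** The document does not suggest selective loss in one arm. The low end of the illustration is close to nominal, and the sign reverses if the arms are swapped.
- **That GEE is unusable without weighting.** Loss explained by modelled terms such as arm and T0 SOC is covered, and a non-independence working correlation removed the bias in this illustration.
- **That a pooled multi-scale test decides the trial.** The wording does not state this, though it does not exclude it.

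**Conclusion.** The point holds in a limited form. The plan fixes a baseline-adjusted comparison of arms but not one analysis for its only primary outcome, and one method it permits would, by default, contradict its intention-to-treat promise.

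The firm part needs no assumption beyond the planned 20% attrition: the contrast, visit and missing-data rule are absent, and a default MANCOVA excludes about 58 of 290. The other sizes are conditional. The 15–44 discarded T1 values depend on the assumed timing of loss. The 0.03–0.12 SD bias depends on an assumed one-arm dropout mechanism. The 8.3–9.8% error depends on ungated testing at both visits. They show what the open wording allows, not what will happen.

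**What to change.** In the Statistical analysis section:

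1. Replace the MANCOVA option with one SOC-only, baseline-adjusted linear mixed model fitted by likelihood, with arm, time (T1, T2), arm-by-time and T0 SOC. Include every randomised participant with any post-baseline SOC value, in the assigned arm. GEE is an acceptable alternative with a prespecified non-independence working correlation, or with weighting or imputation.
2. Before unblinding, name one primary SOC contrast and time point, tested at two-sided 5%, and make the other time point secondary. T1, the end of the intervention, is one possible choice.
3. Add multiple imputation of all randomised participants as a sensitivity analysis, because the main model omits those with no post-baseline SOC.

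This changes analysis wording only and needs no extra participants, visits or data. The sponsor gives up later choice of method and time point, and takes on a little more analysis work.

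Clustering by delivery group (the Experimental group and Control group sections describe group delivery) is a separate issue and should be raised on its own, with its cost. With groups of 6 and an assumed intraclass correlation of 0.05, the design effect is 1 + 5 × 0.05 = 1.25, and power at d = 0.43 falls from about 0.90 to 0.83.

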***Subjective general well-being.*** The 24-item BBC Subjective Well-being Scale (BBC-SWB) will be used to measure the participants' subjective experiences of general well-being (Pontin et al., 2013). It measures three components: psychological well-being, physical health and well-being and relationships with good internal consistency (Cronbach's  $\alpha = .94$ ) and concurrent validity ( $r = .640 - .80$ ) (Pontin et al., 2013). The scale is scored using a 5-point Likert-scale.

**Salivary cortisol:** Salivary cortisol levels (sCort) will be used as a biomarker of psychological stress. sCort is considered a reliable measure of hypothalamus pituitary adrenal axis (HPAA) adaptation to stress and correlates well with plasma cortisol (Nater et al., 2013). Average sCort levels in healthy subjects are 5.52 - 28.92 nM/l in the morning; 1.10 - 11.32 nM/l in the afternoon (Bozovic et al., 2013). sCort is stable for several days, non-invasive and easily obtained without adding stress to subjects (Bozovic et al., 2013), and so is suitable for this study in which the participants are required to provide multiple samples at home. Samples will be collected from saliva using Cortisol Salivary Test kits and analysed using a commercially available enzyme-linked immunoassay (eNano Health). Participants will be asked to provide 2 samples: 0700–0800 h and 1600–1700 h to avoid meals within 60 min of providing each sample and to avoid caffeine-containing food and drink during the two days of sampling. Participants will be instructed to keep the samples in an envelope and send to the laboratory for analysis.

**Demographic information.** A self-developed questionnaire will be used to collect demographic information about the participants, including age, gender, educational level, religious beliefs and practices, socioeconomic status and coping behaviour. The latter will be assessed using the Brief Cope Inventory (COPE) (Carver, 1997).

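### The cortisol ANOVA states no transformation; on raw levels a uniform percentage fall would often show as a group-by-day-by-time interaction, larger in the morning, so log cortisol should be pre-specified

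*Combined protocol and SAP*

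**What the plan says.** The Statistical analysis section gives cortisol its own model: "Repeated measures of ANOVA will be performed to explore the levels of sCort differing within subjects and between groups". The rest of that sentence adds a day factor (two sampling days) and a time factor (five sampling times). The section names no transformation, no distribution check and no target contrast for this model. Its one provision for non-normal data, a Mann-Whitney test, belongs to the simple comparisons of the arms at baseline and at each time point. The section also puts secondary outcomes under a baseline-adjusted MANCOVA or GEE, so cortisol could be analysed in two ways.

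The Salivary cortisol paragraph supplies the only figures on the distribution: "Average sCort levels in healthy subjects are 5.52 - 28.92 nM/l in the morning; 1.10 - 11.32 nM/l in the afternoon". It does not say what kind of interval these are. It asks for two samples, one in the morning and one in the afternoon.

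**The concern.** In a model with a time-of-day factor, the scale decides what an interaction means. Morning cortisol is both higher and more spread out than afternoon cortisol. If the programme lowers cortisol by the same proportion at both times, the fall in nM/l is larger in the morning, and a raw-scale ANOVA has a difference between times to detect. On the log scale the two effects are equal.

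Cortisol is the only physiological outcome named in H2. A raw-scale interaction could be reported as an effect of the programme on the daily cortisol rhythm when the proportional effect was the same all day. Leaving the scale open also allows it to be chosen after the data are seen.

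**Working it through.** **The plan's own figure.** No SD, effect or power is given for cortisol; the only usable design number is the group size. The Sample size section says: "To achieve 90% power to measure outcome three times in two groups, 232 subjects", that is 116 per group. A one-way MANOVA global test with 2 groups, 3 responses and f = 0.25 gives f² = 0.0625, lambda = 0.0625 x 232 = 14.5, df 3 and 228, power 0.902. The figure is reproduced, although this variant does not use the stated correlation of 0.5. Attrition: 116 / (1 - 0.20) = 145 per arm, as stated. I use 116 per arm (completers).

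**What the ranges show.**

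| | Morning | Afternoon | Ratio |
|---|---|---|---|
| Range (nM/l) | 5.52-28.92 | 1.10-11.32 | |
| Midpoint | 17.22 | 6.21 | 2.77 |
| Width | 23.40 | 10.22 | 2.29 |
| Upper/lower | 5.2 | 10.3 | |
| Log width | 1.66 | 2.33 | 0.71 |

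Raw spread rises with level. Logs bring the two spreads closer without making them equal.

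**Effect of a uniform 20% fall.** At the midpoints this is 0.20 x 17.22 = 3.44 nM/l in the morning and 0.20 x 6.21 = 1.24 in the afternoon, a difference of 2.20. On the log scale both changes are ln(0.80), so the difference is zero.

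**Hand check, ranges read as normal 95% intervals.** SDs are 23.40/3.92 = 5.97 and 10.22/3.92 = 2.61. Assume a between-time correlation of 0.3. The SD of morning minus afternoon is sqrt(5.97² + 2.61² - 2 x 0.3 x 5.97 x 2.61) = 5.75. With an assumed between-day correlation of 0.5, its change from T0 to T1 has the same SD, since 2 x (1 - 0.5) = 1. The standard error is 5.75 x sqrt(2/116) = 0.755, so z = 2.20/0.755 = 2.91 and the interaction is declared in about 83% of trials. The artefact therefore does not need log-normality.

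**Simulation, ranges read as log-normal 95% intervals.** Log-SDs are ln(28.92/5.52)/3.92 = 0.42 and ln(11.32/1.10)/3.92 = 0.59. Each person has four samples: morning and afternoon at T0 and T1. This takes the day factor to mean the two visits, which the plan does not say outright. Between-day and between-time correlations are each 0.3 to 0.5 (assumed). The same percentage fall is applied at both times in the intervention arm. The three-way contrast is (AM at T1 - AM at T0) - (PM at T1 - PM at T0), compared between arms at two-sided 5%.

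| Uniform fall | Interaction, raw | Interaction, log |
|---|---|---|
| 10% | 17-26% | about 5% |
| 15% | 37-53% | about 5% |
| 20% | 56-78% | about 5% |

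Across these falls, a significant morning effect with a non-significant afternoon effect and a significant interaction occurs in about 14-30% of raw-scale trials, against 1-3% on the log scale. Power for group x day differs by about 1-5 points in favour of log.

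**Sensitivity, 20% fall, between-day correlation 0.5, between-time 0.3.**

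| Case | Interaction, raw | Interaction, log |
|---|---|---|
| Base | 69% | 5% |
| 145 per arm | 81% | 5% |
| Ranges read as ±3 SD | 99% | 4% |
| Equal log-SD of 0.5 | 57% | 6% |

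**The case against.** Several points against the concern stand.

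- **Silence on the scale.** The plan never says that the levels are untransformed. That is the ordinary reading of the wording, but it is an inference.
- **The interaction is false only if effects are proportional.** A uniform percentage fall is a real difference in nM/l, and no section says that effects should be proportional. The problem has a mirror image: a uniform absolute fall of 0.5 to 1.0 nmol/L gave a log-scale interaction in 33% to 99.6% of simulated trials, against about 5% on raw levels. The log scale carries its own assumption.
- **The ranges are only roughly multiplicative.** Upper-to-lower ratios of 5.2 and 10.3 show that logs do not equalise spread, and the type of interval is not stated.
- **The reach is limited.** Cortisol is secondary, the ANOVA is worded as exploratory, and H2 predicts better cortisol levels, not a changed daily pattern.

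A reader might also infer that a uniform fall would often be reported as a morning-only effect and that logs would prevent this. The figures do not support that. At falls of 10-15%, morning significant with afternoon not significant occurs in 21-41% of raw-scale trials and 23-37% of log-scale trials, because the assumed afternoon log-SD is larger. What the raw scale often produces is an interaction with an apparently larger morning effect. Nor is there a material loss of power for the overall effect.

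**Conclusion.** The point holds as a cheap improvement to a secondary, exploratory analysis. The planned model has a time-of-day factor and no stated transformation, and the protocol's own ranges show spread rising with level. Under a uniform 15% fall, a raw-scale analysis would declare a group x day x time interaction in roughly 37-53% of trials, where the log scale stays near 5%. The rates depend on the assumed meaning of the ranges, the assumed distribution, the assumed correlations, two samples at each of two visits, and a proportional effect. The documents give none of the first three for cortisol. The direction survives every reading of the ranges tried. Log is the better default for a positive, right-skewed measurement, but it is not assumption-free. The primary outcome, sense of coherence, is untouched.

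**What to change.** In the Statistical analysis section:

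1. State that cortisol is analysed as its natural logarithm, in the repeated-measures ANOVA and in any baseline-adjusted model.
2. Report geometric-mean ratios (MB/control) with 95% confidence intervals for the morning and the afternoon samples.
3. Name group x day as the main contrast for H2. Label group x day x time, the change in ln(AM) - ln(PM), as exploratory.
4. Reconcile the sampling schedule and define the day factor. The Salivary cortisol paragraph has two samples, but the analysis section has five sampling times. Study design has cortisol at T0 and T1, but Measures has it at T1. With T1 only, neither the change contrasts nor baseline adjustment could be fitted.

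The cost is a few sentences and one transformation in SPSS, with no new data. Results become ratios instead of nM/l differences, and the report should say that the log scale assumes roughly proportional effects.

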**Study design.** We will conduct a two-arm, parallel randomised controlled trial (RCT) to evaluate the effects of the MB programme. Randomisation involving computer-generated two-digit random numbers (even and odd) (Excel 2007, Microsoft, Redmond, WA, USA) will be used to allocate participants in sequence to either the intervention group or control group in a 1:1 ratio after they have provided consent to participate. The allocation will be blinded to the participants and the data analyst. The random allocation will be conducted by a research assistant who will not be involved in the intervention and data analysis. Participants in the experimental arm will receive a 6-week MB programme. Participants in the control arm will receive a 6-week placebo control programme and will be blinded to the study details. Data will be collected from both groups at three time points: before-intervention (T0), after-intervention (week 6; T1) and 1-month follow-up (week 10; T2), except the salivary cortisol levels which will be assessed at T0 and T1. Figure 2 depicts the flow of the study.

**Subject recruitment.** The participants will be recruited from universities and district

centres through emails, social media, leaflets and posters. Inclusion criteria: young people (aged 18 to 30); moderate level of stress (Perceived Stress Scale (PSS-10) score  $\geq 14-26/40$ ); a liking for music. Exclusion criteria: participants diagnosed with an acute mental problem; participants under the influence of drugs that affect the nervous system; having previous experience with imagery evoked by music and meditations where music is played.

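### The repeated-measures ANOVA named for salivary cortisol, in its standard SPSS form, drops any participant with one missing tube; a mixed model would keep them, but the gain depends on how tubes are lost

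*Combined protocol and SAP*

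**What the plan says.** Statistical analysis declares an "RCT with an intention-to-treat analysis using SPSS, Version 26". For cortisol it names one specific method: "Repeated measures of ANOVA will be performed to explore the levels of sCort differing within subjects and between groups". That sentence goes on to give two within-subject factors, "between the two sampling days (day" and "across the five sampling times (time" (each quote stops before its closing bracket). A more general sentence in the same section offers MANCOVA or GEE, with baseline adjustment, for the primary and secondary outcomes. Cortisol is listed among the secondary outcomes, and H2 names it.

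The Salivary cortisol paragraph says that "the participants are required to provide multiple samples at home", and that participants send them to the laboratory in an envelope. On timing it says "Participants will be asked to provide 2 samples: 0700–0800 h and 1600–1700 h", with instructions "to avoid caffeine-containing food and drink during the two days of sampling".

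On occasions, Study design says that all outcomes are measured three times "except the salivary cortisol levels which will be assessed at T0 and T1". The Measures paragraph gives T1 only.

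The only allowance for loss is the 20% attrition under Sample size. Nothing is said about imputation, missing values, or missed or unusable tubes.

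**The concern.** In its usual SPSS form, repeated-measures ANOVA needs one complete row per participant. A single empty cell removes the person and every other tube that they supplied. Home collection in one-hour windows, under meal and caffeine rules, makes isolated losses foreseeable among people who stay in the trial: a missed window or too little saliva is enough.

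Two things are at stake. Usable cortisol measurements are thrown away, so the arm comparison is less precise than the data allow. And the analysed set becomes those who delivered every tube, which is fixed after randomisation and does not fit the stated intention-to-treat analysis.

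**Working it through.** **The plan's own figure.** Sample size gives 232 evaluable participants (116 per group) and 145 per arm. The 232 reproduces as a global MANOVA test with three responses, f² = 0.25² = 0.0625, λ = 0.0625 × 232 = 14.5, df (3, 228), 5% level and 90% power. Then 116 / (1 − 0.20) = 145, and 2 × 145 = 290. These figures are not in dispute. They do not concern cortisol and do not allow for single-tube loss.

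**Inputs from the documents.** 145 per arm (Sample size); two-sided 5% level (Sample size); correlation 0.5 (Sample size, borrowed, because it was not stated for cortisol tubes); T0 and T1 (Study design).

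**Assumptions.** Tube-loss rate q = 2%, 5% or 10%, since the documents give none; no visit dropout; equal variances; equal correlation between all tubes.

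**Tubes in a complete set, k.**
- 4: two windows on one day at each of T0 and T1.
- 8: two windows on two days at each visit.
- 10: the analysis sentence's two days by five times, here taken as one day per visit.

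**Step 1: share with a complete set.** With independent loss this is (1 − q)^k. At q = 5%: 0.95⁴ = 0.815, or 236 of 290; 0.95⁸ = 0.663, or 192; 0.95¹⁰ = 0.599, or 174. If a whole visit envelope is lost with probability q, it is (1 − q)² whatever k is: 0.95² = 0.9025, or 262.

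**Step 2: variance of the group-by-visit effect.** With m tubes per visit, a participant's difference between visit means has variance 2(1 − 0.5)/m = 1/m, in units of the tube variance. The complete-case variance is therefore 2 / (m × 145 × share complete).
- m = 2: 2 / (2 × 145 × 0.8145) = 0.00847.
- m = 4: 2 / (4 × 145 × 0.6634) = 0.00520.

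For all available tubes, sum X′V⁻¹X over every missing-tube pattern, weighted by its probability. V has 1 on the diagonal and 0.5 elsewhere. The fixed effects are arm, visit, arm-by-visit and window. Inverting gives 0.00736 (m = 2) and 0.00365 (m = 4). The ratio R is 0.00847 / 0.00736 = 1.15 and 0.00520 / 0.00365 = 1.42.

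**Step 3: power.** Take an effect with 90% power when all available tubes are used. Complete-case power is Φ((1.960 + 1.2816)/√R − 1.960).
- R = 1.15: Φ(3.021 − 1.960) = Φ(1.061), about 86%.
- R = 1.42: Φ(2.718 − 1.960) = Φ(0.758), about 78%.

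| Loss pattern | k | q | Complete, of 290 | R | Power |
|---|---|---|---|---|---|
| Independent tubes | 4 | 2% | 267 | 1.06 | 88% |
| Independent tubes | 4 | 5% | 236 | 1.15 | 86% |
| Independent tubes | 4 | 10% | 190 | 1.34 | 80% |
| Independent tubes | 8 | 2% | 247 | 1.15 | 86% |
| Independent tubes | 8 | 5% | 192 | 1.42 | 78% |
| Independent tubes | 8 | 10% | 125 | 2.06 | 62% |
| Independent tubes | 10 | 5% | 174 | 1.58 | 73% |
| Whole envelope | 4 | 5% | 262 | 1.02 | 89–90% |
| Whole envelope | 8 | 5% | 262 | 1.01 | 90% |
| Whole envelope | 4 | 10% | 235 | 1.04 | 89% |
| Whole envelope | 8 | 10% | 235 | 1.02 | 89% |

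Envelope loss costs little because a participant seen at only one visit carries little information on change between visits. Real loss would lie between the two patterns. If cortisol were taken at T1 only, with two tubes, 262 of 290 would be complete at 5% independent loss, and there would be no group-by-visit effect to estimate.

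**The case against.** The strongest reply is that the ANOVA need not be the test of H2 at all. The plan uses it only to explore cortisol levels, and the general sentence may cover cortisol as a secondary outcome; GEE would keep partial records. This stands in part. A reader might infer that the whole biomarker hypothesis rests on the ANOVA, and the documents do not support that. But the general sentence leaves the choice open, MANCOVA also deletes incomplete rows, and the ANOVA is the only method named for cortisol itself.

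Deletion is also inferred from how the named procedure normally works; the plan does not state it. That is fair, but nothing in the plan overrides it.

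The size rests on assumptions. Samples travel in an envelope, so loss in transit may take a whole visit's tubes, and then almost nothing is lost in precision. The 0.5 was set for an outcome measured three times, not for cortisol tubes. The quoted healthy ranges (5.52–28.92 in the morning, 1.10–11.32 in the afternoon) make equal variances doubtful. These points stand, and they are why a range is given.

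A reader might also infer that deletion will differ by arm, because the music breathing arm meets weekly and controls meet in weeks 1 and 6. The documents do not establish this: both arms get reminders, and T0 tubes precede the intervention. Nor can one say that planned cortisol power is lost, since none is claimed.

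**Conclusion.** The concern holds in a limited form. The one method named specifically for cortisol deletes partial records in its standard form, no missing-tube rule exists, and this does not fit the intention-to-treat statement. At an assumed 5% loss with T0 and T1 sampling, 290 participants and correlation 0.5, the variance inflation runs from about 1.01–1.02 (whole envelopes lost) to 1.15 for 4 tubes or 1.42 for 8 tubes (independent loss). Power of 90% then becomes anything from about 90% down to 86% or 78%. The figure cannot be narrowed until the schedule is settled, because the documents disagree on both the occasions and the number of samples. Bias between arms is possible but not shown. The matter affects a secondary outcome and leaves the primary outcome and the sample size untouched.

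**What to change.** First reconcile the cortisol schedule across Study design, Measures, Salivary cortisol and Statistical analysis: which occasions, how many days, and how many samples per day.

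Then replace the cortisol repeated-measures ANOVA with a linear mixed model (SPSS MIXED) on individual tubes:
- Fixed effects for arm, visit, sampling window and arm-by-visit. The interaction is essential: without it, the arm effect is averaged over T0 and T1, and any treatment effect is diluted by baseline.
- A participant random effect plus a participant-by-visit effect, or an equivalent covariance that allows clustering within a visit and unequal morning and afternoon variance.
- The estimate is the arm difference at T1, adjusted for baseline or with the arms constrained equal at T0.
- Include every randomised participant with at least one valid tube, analysed as randomised.
- Report valid tubes by arm, visit and window.

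If the reconciled schedule has T1 only, the visit and baseline terms fall away, and arm and window remain. State also that this model, and not the general MANCOVA or GEE sentence, governs cortisol.

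The cost is a few sentences. The named software has the procedure and no new data are needed. The small downside is reliance on tubes being missing at random given the observed data.
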